To assess preliminary efficacy in terms of within-group improvement.	Efficacy outcomes focusing on general anxiety, depressive symptoms, the fear of cancer recurrence, and quality of life

Methods

[figure not shown]
Design

This is a randomized factorial trial (N=400; 2x2x2 with a cell size of 50; for the pilot study: N=48; 2x2x2 with a cell size of 6) of therapist-guided Internet-delivered psychological treatment for cancer survivors with long-term clinically significant anxiety or depression despite a good prognosis. Study site is Karolinska Institutet, Stockholm, Sweden. The sample size allows for two-sided conventional mean tests of small ($d \approx 0.3$) component effects (n=200 vs. 200) with 80% power of, given an alpha of 5% and up to 14% missing data post-treatment. The pilot study will have a feasibility focus, though the sample size will also be sufficient to study average within-group effects with 80% power in two-sided tests of moderate effects ($d \approx 0.45$) on efficacy outcomes measured at two time points, given a 5% alpha and up to 20% missing data post-treatment. The study protocol will be reviewed by the Swedish Ethical Review Authority and preregistered at ClinicalTrials.gov. All procedures will adhere to the declaration of Helsinki and the relevant privacy and data management legislation.

Eligibility criteria

- a) Cancer survivor 0.5-20 years after main therapy. For the pilot study: survivor of breast cancer (n=24), testicular cancer (n=12), or thyroid cancer (n=12),
- b) Clinically significant anxiety or depression (PHQ-9 ≥ 10 , or GAD-7 ≥ 8) (24, 25)
- c) At least 18 years old
- d) Resident of Sweden (listed and de facto). For the full trial: Stockholms län, Västra Götalands län, or Skåne län.
- e) Sufficient technical knowledge and knowledge of the Swedish language to take part in a text-based online treatment
- f) Continuous access to an electronic device that can be used to access the study web platform
- g) Not recurrent thoughts of suicide, as based on clinical judgement aided by the structured interview (see below) and the MADRS-S item 9
- h) No severe medical condition (e.g., very poor prognosis, stage IV cancer), severe psychiatric disorder (e.g., psychotic disorder, bipolar disorder, or severely debilitating substance use disorder, severe depression), or medical treatment (e.g., chemotherapy, immunotherapy, radiotherapy) that makes the treatment unfeasible
- i) No other ongoing psychological treatment

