- j) Either no continuous psychotropic medication, or continuous psychotropic medication stable for the past 4 weeks, and expected to remain so during the intended treatment period
- k) Not planned absence for more than one week of the intended treatment period
- l) Complete pre-treatment assessment and subsequently randomized to a condition

Figure 1. Study flowchart

Procedure

Recruitment

The study will be advertised via oncology clinics, patient organizations, and social media. We also aim to inform the participants in an ongoing cohort study of thyroid cancer who previously, as part of that project, indicated that they were interested in psychological treatment (2014/714-31, with a separate amendment that will be submitted for this purpose). On the secure study web platform, self-referred individuals are presented with written information about participation in the study including data management procedures and their right to drop out of the study at any point, and how to get in contact with the research group. Applicants provide informed consent via a secure web form. This procedure for obtaining informed consent is widespread and has been used in several previous online treatment trials (e.g., 2014/1530-31/2, 2020-01740, 2021-01400). After having provided informed consent applicants complete a screening battery which includes validated online questionnaires (Table 2) and standard questions about key demographic and clinical characteristics. Applicants who, based on their replies, are subject for immediate exclusion based on criterion a, b, c, d, g, or h (see above) are informed of this and referred to routine care services by means of a standardized e-mail. The remaining applicants are contacted for a brief psychiatric interview with a psychologist or physician working under the supervision of the principal investigator. This interview establishes eligibility and is based primarily on the Mini-International Neuropsychiatric Interview (26) with a separate module for the assessment of pathological health anxiety (Open Science Framework identifier: t3yvz). Information from the interview and screening battery is also used to describe the final sample in terms of sociodemographic and clinical characteristics.

Measurements

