a) Patients with heightened scores are assessed by a clinician, and referred to routine care services if necessary

b) For the weekly (non-screening) measurements, rephrased to concern the past week.

Treatment conditions

General format of Internet-delivered treatment

Therapist-guided online treatment is delivered over 10 weeks, which is proven format (18) recommended for cancer survivors (20). The patient regularly logs in to the encrypted web platform (“BASS”, as provided via the Karolinska Institutet eHealth core facility). Most of the treatment content is conveyed via an illustrated text divided into modules, equivalent of book chapters. Each modules contains an educational text, homework assignments, and questions for reflection. Participants communicate with their therapist via a system reminiscent of email, and receive a reply within about two weekdays. Homework exercises are tailored to the individual needs of the patient. In total, eight modules are completed at a pace of about one module per week. Participants gain access to new models contingent on progress. Therapists receive continuous supervision from the principal investigator.

Open access publication of treatment content

In order to promote transparency and contribute to the research field as well as clinical practice, the treatment content from this pilot study will be transferred to the public domain and published open access online, tentatively via the Open Science Framework (OSF).

Randomized allocation of treatment components

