In order for the analysis of treatment components to be valid and helpful in the design of future therapies, it is important that the participants remain blinded to the randomized factorial design throughout the full measurement period. (Full blinding, i.e., where the patient and therapist remain unaware of the treatment condition, is not possible in psychological treatment research (48).) Regardless of condition, participants will be informed that they take

part in an Internet-delivered support program for improved mood in the aftermath of cancer. At the 12-months follow-up (3 months in the pilot study), a written blinding check will then be conducted whereby participants are asked about whether they are aware of which treatment variants that are being compared and why. Participants will then be unblinded (debriefed) and those in the attention control (see above) will be offered the full material from the full factor version of the treatment.

Secondary outcome: registry data on healthcare consumption

If funding is secured for this secondary outcome, registry data on health care consumption will also be collected, pertaining to the 2 years immediately before treatment, and the 2 years immediately following treatment. To ensure access to health consumption data, patients will be recruited exclusively from Stockholms län, Västra Götalands län, and Skåne län for the full trial. This will not be implemented in the pilot study.

Data safety and management

Throughout the project, data management plans and documentation will be maintained and revised in accordance with up-to-date guidelines of Karolinska Institutet. The study web platform will employ encrypted traffic and two-factor authentication. Researchers in the project have access to study data, which is stored and managed in accordance with European Union and Swedish data protection and privacy legislation, and the guidelines of Karolinska Institutet. Personal data are exclusively stored in systems classified and provided specifically for this purpose by Karolinska Institutet. Study results are reported in a manner that does not make it possible to identify individual participants.

Statistical analysis

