Preparatory work in terms of writing protocols, producing content, and submitting the work for ethical review will take place in May-September 2023. We plan to involve patient representatives in the treatment drafting process. Hands-on procedures are first evaluated, and recruitment is initiated, in September 2023. Recruitment for the pilot trial is complete around the end of 2023. The finalization of all routines for the full-scale trial, including the recruitment of additional psychologists interested in contributing to the project by serving as therapists in exchange for co-authorship, will be completed during the January-June period. Recruitment of participants for the full-scale randomized factorial trial will begin in August 2024. From then on, approximately 80 participants will be recruited each semester until the end of 2026. We expect the last 12-month follow-up assessment to be completed in December 2027. Manuscripts will be submitted for publication throughout 2028 to 2030.

Significance

This project can lead to substantial societal gains. The population of cancer survivors who experience long-term distress is substantial, and access to structured treatment is insufficient. Internet-delivered psychological treatment is relatively easy to scale up and disseminate, for example in the primary care context, and the development of a free-to-use treatment protocol based on rigorous evaluation in clinical trials could potentially have pervasive effects on suffering and health care utilization. Though the project will proceed in accordance with this research plan, the outcome of the pilot study can also inform the precise design of the full-sized clinical trial and sufficient amendments will be submitted for ethical review as deemed necessary. Experiences from the randomized factorial trial can inform clinical practice in that we will arrive at an evidence-based Internet-delivered psychological treatment for cancer survivors with clinically significant psychiatric symptoms.

References

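### The full trial's eligibility criteria do not exclude pilot participants, who by then have been debriefed about the factorial design the plan wants kept blinded

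*Combined protocol and SAP*

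**What the plan says.** The section Eligibility criteria gives a single list, a to l, for both studies. Differences between them are marked only in criterion a (pilot cancer types) and criterion d ("For the full trial: Stockholms län, Västra Götalands län, or Skåne län"). For the full trial, criterion a is simply "Cancer survivor 0.5-20 years after main therapy", which takes in the breast, testicular and thyroid survivors of the pilot. Criterion i reads "No other ongoing psychological treatment". No criterion refers to taking part in the pilot, earlier access to the programme, or knowledge of the design.

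The section Partial blinding of study design states that, for the component analysis to be valid and useful, "it is important that the participants remain blinded to the randomized factorial design throughout the full measurement period". It then places a blinding check at the last follow-up, which is 3 months in the pilot and 12 months in the full trial, and continues: "Participants will then be unblinded (debriefed) and those in the attention control (see above) will be offered the full material". The section Randomized allocation of treatment components adds that controls cross over to a+b+c, without therapist support, after follow-up.

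On timing, the timetable paragraph just before Significance has pilot recruitment complete around the end of 2023 and says "Recruitment of participants for the full-scale randomized factorial trial will begin in August 2024". It continues until the end of 2026. The Recruitment section describes one set of channels, with self-referral, for both studies.

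**The concern.** The plan makes blinding to the factorial design a condition of a sound component analysis. It also creates a group of up to 48 people who have had the design explained to them, and it leaves the full trial open to them. Those who still have symptoms above the threshold have a reason to reapply, and they know where to do so.

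Two things are at stake. First, a re-entrant knows from the first day that treatment variants are being compared. In a trial with self-reported outcomes this can colour credibility ratings, expectancy and symptom reports. Second, a re-entrant may already have received a component and then be randomised to a cell coded as lacking it. Randomisation balances such people between the two sides of a contrast, so they do not favour either side, but they dilute the contrast.

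**Working it through.** **1. Can a pilot participant pass the list?** Read criterion by criterion, completing the pilot does not disqualify anyone.
- Criterion a: the pilot cancer types fall within the full-trial definition.
- Criterion b: depends on current PHQ-9 (at least 10) or GAD-7 (at least 8).
- Criterion d: requires residence in one of three counties.
- Criterion i: covers treatment in progress, and the pilot treatment has ended.
- The remaining criteria concern age, language, device access, suicidality, severe illness, medication, absence and completion of the pre-treatment assessment.

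The screening described under Recruitment checks a, b, c, d, g and h automatically. It then uses an interview based mainly on the MINI, with a health anxiety module. No question about earlier participation is described.

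**2. Does the timetable allow it?** Pilot recruitment ends about 31 December 2023. Adding 10 weeks of treatment gives about 10 March 2024, and adding 3 months of follow-up gives about 10 June 2024. Allowing a short lag before treatment starts, debriefing is complete by about mid-June, roughly 1.5 months before August 2024. Because full-trial recruitment runs to the end of 2026, a slower pilot would not close the window.

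**3. The plan's own power figure.** Inputs from the section Design: d = 0.3, 200 vs 200, two-sided alpha 5%, up to 14% missing.
- n per side with data = 200 × 0.86 = 172.
- Power ≈ Φ(d × √(n/2) − 1.96) = Φ(0.30 × √86 − 1.96) = Φ(2.782 − 1.960) = 79.4%.

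This reproduces the stated 80%.

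**4. How many re-entrants could already have had a given component?** The pilot is 2x2x2 with 6 per cell. Any one component is assigned in 4 of the 8 cells: 4 × 6 = 24 people. The 6 null-cell controls may receive all components at crossover: 24 + 6 = 30. If all 48 re-entered, the share of the full trial is 30/400 = 7.5%.

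**5. Effect on the contrast.** Assume that a re-entrant who has already had the component shows no further effect of it, and that the SD is unchanged. With m such people among 400, d = 0.30 × (1 − m/400).

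| m | share | d | power (172 per side) |
|---|---|---|---|
| 0 | 0% | 0.300 | 79.4% |
| 5 | 1.25% | 0.296 | 78.4% |
| 12 | 3.0% | 0.291 | 77.0% |
| 30 (ceiling) | 7.5% | 0.278 | 73.0% |

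Ceiling row: 0.30 × 0.925 = 0.2775; Φ(0.2775 × √86 − 1.96) = Φ(2.573 − 1.960) = 73.0%. The documents give no re-enrolment rate, so m = 5 and m = 12 are illustrations only.

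**The case against.** The strongest reply is that the gap is small and will be closed in due course. The document describes its analysis plan as rudimentary. Full-trial routines are to be finalised in January to June, and amendments are promised as the pilot informs the design. Re-entry also needs more than a high score and the right county: the person must meet every other criterion and pass the interview, and a control still working through the crossover material might fail criterion i. The blinding check would also reveal knowledge of the design.

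Part of this stands. Realistic overlap is likely to be well below 48 and its effect on d slight. But the general promise of amendments does not name this gap, and the full-trial check comes at 12 months, after the outcomes have been collected, so it can detect a breach but not prevent one.

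A reader might also infer several stronger points that the documents do not support:
- *That recent outside psychological treatment raises the same problem.* It does not reveal this trial's design, and randomisation balances such exposure on average. Criterion j ("continuous psychotropic medication stable for the past 4 weeks") concerns stability of continuing medication. It is not a washout and sets no precedent for a 4-week window after therapy.
- *That open publication of the pilot content should be embargoed.* The plan says "the treatment content from this pilot study will be transferred to the public domain and published open access online" but gives no date, and open access is a deliberate commitment. Counting the 400 − 50 = 350 people not assigned a+b+c says nothing about how many would find or use the material.
- *That dilution could reach 48/400 = 12% (d = 0.264).* This treats every pilot participant as having had every component, whereas at most 30 have had any given one.

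**Conclusion.** The omission is real. The criteria as written admit people who have been debriefed and already treated, against the plan's own statement that blinding to the design matters for the component analysis. The case for acting rests on that unprotected condition more than on lost power. The dilution has a ceiling of 7.5% of participants per component contrast, taking d from 0.30 to about 0.278, and is probably much smaller.

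The conclusion assumes that pilot treatment starts soon after recruitment ends, although a delay would not change it given recruitment to the end of 2026. The ceiling further assumes that all 48 re-enter, that all 6 controls take up the crossover, and that prior receipt removes the component's effect entirely. The reading rests on the text of the criteria list, which runs unbroken from a to l; the flowchart in Figure 1 could not be read.

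**What to change.** Add one exclusion to the full-trial criteria: *previously randomised in IN-FACT-0*. Check each applicant against the pilot participant list at screening, before the interview.

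The cost is one criterion and one list check. At most 48 people are lost from the recruitment pool. Sample size, alpha and planned power are unchanged. The change can go into the amendment that the plan already foresees after the pilot, provided it is in force before recruitment opens in August 2024.

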Participants complete validated self-report questionnaires at screening, before treatment, each week during treatment, after treatment, and 3 months after treatment. These are administered online in Swedish (Table 2). In the pilot study, follow-up will take place 3 months after treatment (not at 6 or 12 months).

Table 2. Validated self-report questionnaires administered in the study

Questionnaire	Outcome	Ref	SN	PRE	WK	PST	6MFU	12MFU
Screening and safety only								
Alcohol Use Disorders Identification Test (AUDIT)	Alcohol use	(27)	x					
Drug Use Disorders Identification Test (DUDIT)	Drug use	(28)	x					
Hospital Anxiety and Depression Scale (HADS)	General distress	(29)	x					
Montgomery-Åsberg Depression Rating Scale item 9	Suicidal ideation ^a	(30)	x	x	x	x		
Symptom domains and similar								
36-Item Short Form Health Survey (SF-36)	Health-related quality of life	(31)		x		x		
7-item general anxiety questionnaire (GAD-7)	General anxiety	(32)	x	x ^b				
9-item Patient Health Questionnaire (PHQ-9)	Depression symptoms	(33)	x	x ^b				
9-item Fear of Cancer Recurrence Inventory (FCRI-9)	Fear of cancer recurrence	(34)		x	x	x	x	x
14-item Health Anxiety Inventory (HAI-14)	Health anxiety	(11)		x		x	x	x
Somatic Symptom Scale 8 (SSS-8)	Somatic symptom burden	(35)		x		x	x	x
Body Image Scale (BIS)	Body image	(36)	x			x		
12-item WHO Disability Assessment Schedule 2.0 (WD2-12)	Disability	(37)	x	x		x	x	x
Process and target variables								
3-item Behavioral Activation for Depression Scale – Activation (BADS-AC-3)	Behavioral activation	(38)		x	x	x	x	x
Symptom preoccupation scale (SYMPs)	Symptom preoccupation	Not yet published		x	x	x	x	x
Godin-Shephard Leisure-Time Physical Activity Questionnaire (GSLTPAQ)	Physical activity	(39)		x	x	x	x	x
Adapted self-efficacy scale	Self-efficacy	(40)		x	x	x	x	x
Credibility/Expectancy scale (C/E scale)	Credibility and expectancy	(21)			w. 2			
Working Alliance Inventory (WAI)	Relationship with the therapist	(41)			w. 2			
Explicit evaluation of therapy								
8-item Client satisfaction questionnaire (CSQ-8)	Satisfaction with treatment	(22)				x		
20-item Negative Effects Questionnaire (NEQ-20)	Negative effects of treatment	(23)				x		
Cost-effectiveness outcomes								
EuroQol 5D (EQ5D)	Utility score	(42)		x		x	x	x
Trimbos questionnaire (TIC-P)	Resource use	(43)		x		x	x	x

SN = screening, PRE = pre-treatment, WK = weekly, PST = post-treatment, 6/12MFU = 6/12-months follow-up

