The following randomization procedure will be piloted: Each cohort size is a multiplier of the number of unique combinations of treatment components (i.e., 8). After completion of the pre-treatment assessment, and separately for each cohort, randomization is achieved using a true random number service (www.random.org), managed by an individual otherwise not involved in the trial. Tentatively, based on the outcome of the 2023 pilot trial and feasibility outcomes, interventions will be built using the following components derived from existing protocols: (a) behavioral activation with existential themes and emphasis on values (44, 45) and relationships, (b) systematic exposure with mindfulness training with a focus on anxiety about health and/or death (46), body image, and cancer-related trauma, and (c) an overview of self-management techniques in terms of physical exercise, dietary advice, and strategies for improved sleep. Fifty patients are randomized to each combination of treatment components: a, b, c, a+b, a+c, b+c, a+b+c, and also a null group where support and rudimentary clinical information is given to control for the effect of attention from a clinician and enrollment in the structured online format, resulting in the total sample size of 400. The point of administering all these combinations is to make it possible to model the simple effect (added contribution) of each component to the treatment effect, and also all component interactions. After the follow-up phase (see below), for ethical reasons, controls are crossed over to the a+b+c combination though without therapist support. To the extent that this is found feasible in the pilot study, the treatment content for all combinations of components will be developed with similar readability (47), interactivity, and picture content. Importantly, even in the null group attention control, the treatment will involve support from a clinician, information about the negative long-term effects of cancer and will offer participants the possibility of observing their own symptoms in a systematic manner.

Partial blinding of study design

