The main pre-post efficacy outcomes will be analysed by an individual blinded to treatment identity (each component is coded simply as -0.5 vs. 0.5 without labels in the dataset). Hierarchical multiple imputation by chained equations will be employed to manage missing data, and imputation will be conducted separately for each cell so as to maintain interaction effects (49). Efficacy outcomes are analysed using fully factorial linear mixed models, so that the simple effects of the components, and also their interactions, can be quantified and tested. Health economic analyses will focus on comparing the most potent treatment configuration (cells are collapsed if no component shows superiority) to the null group (i.e., rudimentary information and support from a clinician only). Mediation analysis will be conducted within a structural equation modelling framework, based on parallel process growth models. The pilot study will not focus on inferential statistics, but rather the feasibility outcomes (see Table 1).

Ethical considerations

This randomized factorial trial and the pilot study are conducted in accordance with the declaration of Helsinki, current Swedish and European Union privacy and data management legislation, and internal guidelines of Karolinska Institutet. The project will be preregistered online, and results including the treatment content will be published open access so as to ensure transparency and that findings benefit the research field. Applicants will be required to provide informed consent in order to be included as participants.

Psychological treatments can induce unwanted effects for example in terms of deterioration or an increase in symptoms, disappointment with the quality of treatment, dependency on the therapist, stigma associated with enrollment, hopelessness as a consequence of insufficient efficacy, or a sense of failure or reduced self-efficacy (50). Based on the existing evidence base, the negative effects of therapist-guided Internet-delivered psychological treatments

similar to that evaluated here are typically limited (51, 52). In contrast, the beneficial effects for example on anxiety are more likely to be at least moderately sized on average. Adverse events and participants mood is tightly monitored throughout the intervention. Heightened suicidal ideation is automatically flagged and cause for clinical assessment. Participants are referred to routine services if necessary.

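### Full trial: MADRS item 9 is last scheduled at post-treatment, so the 50 controls are offered the unguided a+b+c programme on a reading about 12 months old

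*Combined protocol and SAP*

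**What the plan says.** All references are to the combined protocol and SAP.

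- **Table 2 (Measurements).** The row "Montgomery-Åsberg Depression Rating Scale item 9" is marked at SN, PRE, WK and PST. Its 6MFU and 12MFU cells are empty.
- **Table 2, footnote a**, which is attached to that row alone: "Patients with heightened scores are assessed by a clinician, and referred to routine care services if necessary".
- **Eligibility criteria, g.** Entry to guided treatment required: "Not recurrent thoughts of suicide, as based on clinical judgement aided by the structured interview (see below) and the MADRS-S item 9".
- **Randomized allocation of treatment components.** On the null group: "After the follow-up phase (see below), for ethical reasons, controls are crossed over to the a+b+c combination though without therapist support".
- **Partial blinding of study design.** After the blinding check at the 12-month follow-up, participants are debriefed and "those in the attention control (see above) will be offered the full material from the full factor version of the treatment".
- **Ethical considerations.** "Adverse events and participants mood is tightly monitored throughout the intervention", followed by "Heightened suicidal ideation is automatically flagged and cause for clinical assessment".

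**The concern.** Before guided treatment, the plan screens for suicidality with item 9 and a clinical interview. During treatment it repeats item 9 every week. Controls meet the active content much later and with no therapist, and the plan describes no equivalent check at that point.

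The content is not neutral. Component b includes exposure work on fear of death and on trauma from the cancer. The people offered it entered with clinically significant anxiety or depression and have until then received only the attention-control programme. The Ethical considerations section itself lists hopelessness after an ineffective treatment among the possible unwanted effects.

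A control whose suicidal ideation has risen since post-treatment could complete the 12-month battery, be debriefed and receive the material without answering the one item that footnote a acts on. This is a matter of patient safety. It does not affect bias, alpha or power.

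**Working it through.** **Inputs from the documents**
- Full-trial N = 400 in a 2x2x2 design with 50 per cell (Design).
- Treatment lasts 10 weeks (General format of Internet-delivered treatment).
- Follow-up is counted in months after treatment (Measurements).
- The offer to controls comes at debriefing, after the 12-month blinding check (Partial blinding of study design).

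**Inputs assumed here**
- 1–5% of item-9 readings are heightened.
- 70–100% of participants complete the 12-month battery.
- The documents give neither figure. The 14% missing-data allowance in Design refers to post-treatment only.

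**1. Number of controls.** 2 x 2 x 2 = 8 cells, and 400 / 8 = 50, which agrees with the plan. The other seven cells hold 400 − 50 = 350. Fifty is the number randomized; fewer may remain at 12 months.

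**2. Is a follow-up battery already sent?** Rows marked at both 6MFU and 12MFU are FCRI-9, HAI-14, SSS-8, WD2-12, BADS-AC-3, SYMPs, GSLTPAQ, self-efficacy, EQ5D and TIC-P: 10 questionnaires. Item 9 is marked at 0 of the 2 points.

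**3. Age of the last scheduled reading at the offer**
- 12MFU counted from the end of treatment, as Measurements implies: about 12 months.
- 12MFU counted from baseline: 10 weeks = 70 / 30.4375 = 2.3 months, and 12 − 2.3 = 9.7 months.
- Item 9 added at 6MFU only: about 6 months.
- Item 9 added at 12MFU: about 0 months.

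Only the 12-month reading is current when the material is offered. Once it exists, a 6-month reading adds little for this purpose.

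**4. Expected yield among controls**
- Readings: 50 x 0.70 = 35 to 50 x 1.00 = 50.
- Flags: 35 x 0.01 = 0.35 to 50 x 0.05 = 2.5, so about 0 to 3.

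**5. Yield if the item goes to everyone at 12MFU**
- Readings: 400 x 0.70 = 280 to 400.
- Flags: 280 x 0.01 = 2.8 to 400 x 0.05 = 20, so about 3 to 20, including the controls in step 4.

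**The case against.** **The schedule is consistent with itself.** Item 9 sits among the screening and safety measures, monitoring is promised for the duration of the intervention, and Table 2 delivers that. This stands. A reader might infer that the plan breaks a safety commitment to all 400 participants, but it does not. Ending item 9 with treatment is a coherent choice for the 350 who are scheduled for nothing further. Controls differ because the trial schedules new content for them.

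**Other safeguards may exist.** The sentence on automatic flagging names no instrument and no end date. The PHQ-9 row is broken in the extracted text, so PHQ-9 may be collected at follow-up. The adverse events questionnaire in Table 1 has no stated timing, and participants are told how to reach the research group. It therefore cannot be said that nothing would catch a deterioration. But a flag needs a measurement, none is scheduled for item 9 after PST, and no clinician rule is attached to PHQ-9. The item-9 row itself reads cleanly, with four separate marks and two empty cells.

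**The full-trial design is provisional.** The Significance section foresees amendments after the pilot. This is true, and it makes the change easier to adopt.

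**The remedy is limited.** One reading at the offer monitors nothing during the unguided work. Nor can it truly gate access, because "the treatment content from this pilot study will be transferred to the public domain and published open access online". Both points stand. The value lies in one clinical contact with a person who scores high.

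**The pilot.** A reader might infer the same gap there. Table 2 has no 3-month column, so the pilot's follow-up battery is unstated, and the documents do not show that item 9 is left out.

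**Conclusion.** The point holds for the full trial and for the null group. The only questionnaire with a stated clinician action stops at post-treatment. Fifty controls are later offered an unguided programme when their last scheduled reading is about 12 months old (9.7 on the less likely anchor), and no re-check is described. Confidence is high for the empty cells and moderate for the safety consequence.

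The benefit is real but small. About 0 to 3 controls would be flagged under the assumed rates, and entry already excluded recurrent suicidal thoughts and severe depression. The change is worth making because the outcome is serious and the procedure already exists. The documents do not support a case for a 6-month reading, a change to the pilot or a claim of neglect toward the other 350 participants.

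**What to change.** In Table 2, mark MADRS item 9 at 12MFU with footnote a applying, at minimum for the null group. State that the reading is reviewed when the a+b+c material is offered to controls. If a control did not complete the 12-month battery, send the single item with the offer. A heightened score leads to the clinician assessment already described, and the sponsor's thresholds and actions stay as they are.

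Cost:
- One item in a battery already sent: up to 50 administrations for controls only, or up to 400 if everyone receives the same battery.
- About 0 to 3 clinician assessments among controls, or about 3 to 20 if all participants are asked, on the assumed rates.
- Clinician cover until the last 12-month follow-up, expected in December 2027.
- One line in an ethics amendment of the kind the Significance section already foresees.

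Item 9 would be acted on after the 12-month questionnaires are completed, so those outcomes are not disturbed. Sample size, power and the primary analysis do not change.
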